2.4.4.2 Analyses of secondary efficacy endpoints

2.4.4.2.1 Absolute/percent change from baseline for continuous endpoints

The key secondary endpoint, percent change from baseline in pre-bronchodilator FEV1 at Week 12, will be analyzed in the same way as for change from baseline in FEV1 at Week 12, with the only difference that percent changes, instead of absolute changes, from baseline in FEV1 up to Week 12 will be included as the response variables. MMRM model including measurements up to Week 52 will also be used to derive LS mean change at all time-points. Differences in LS means, the corresponding 95% CI and the p-value will be provided for comparisons of each dupilumab dose against its matching placebo along with descriptive statistics.

Change from baseline in ACQ-5 and AQLQ at Week 24 will be analyzed using MMRM including change from baseline up to Week 24 as response variables, regardless if the patient is on treatment or not when the endpoint is measured. The model will include treatment, age, region (pooled country), baseline eosinophil strata, baseline ICS dose level, visit, treatment by-visit interaction, baseline endpoint value, and baseline-by-visit interaction as covariates. MMRM model including measurements up to Week 52 will also be used to derive LS mean change at all time-points. Differences in LS means, the corresponding 95% CI and the p-value will be provided for comparisons of each dupilumab dose against its matching placebo along with descriptive statistics.

Change from baseline in other continuous endpoint at all time-points will be analyzed using MMRM model including measurements up to Week 52. The model will include change from baseline in the endpoint values from Week 2 to Week 52 as response variables, regardless if the patient is on treatment or not when the endpoint is measured, and treatment, age, sex, baseline height, region (pooled country), baseline eosinophil strata, baseline ICS dose level, visit, treatment by-visit interaction, baseline endpoint value and baseline-by-visit interaction as covariates. Sex and baseline height will be included as covariates only in the models for spirometry parameters. Differences in LS means, the corresponding 95% CI and the p-value will be provided for comparisons of each dupilumab dose against its matching placebo along with descriptive statistics.

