2.5.4 Windows for time points

For the safety assessment, the reference date for the derivation of relative days of events or findings will be the date of first IMP administration. Selected safety variables will be summarized by the analysis window define in [Table 8](#) for the by visit descriptive analysis. All available values from central lab will be assigned to the appropriate visit window. In the event of multiple measurements of the same test in the same window, the one closest to the targeted visit date will be used for the by-visit summary. If they are at the same distance to the target day, the latest one will be used. For procedures planned on Visit 2, if it is done on the same date as the first IMP injection but the performance time is missing, it will belong to Visit 2 time window.

Table 8 – Time window for safety endpoints

Visit	Target Day	Time windows for							
		Vital signs	ECG endpoints	Clinical lab testing	Serum Pregnancy test	Urine Pregnancy test	Urinalysis, Serum immunoglobulins	Hepatitis B viral load	Hepatitis screen, HIV screen, ANA and Anti-ds DNA antibody
Visit 1 (Week -4±1)	-28±7	<-14	1-	<-14	1-		1-		1-
Visit 2 (Week 0)	1	-14-1-		-14-1-		1-		1-	
Visit 3 (Week 2)	15	1+-21	1+-21						
Visit 4 (Week 4)	29	22-35	22-56	1+-42		1+-42			
Visit 5 (Week 6)	43	36-49							
Visit 6 (Week 8)	57	50-63		43-70		43-70			
Visit 7 (Week 10)	71	64-77							
Visit 8 (Week 12)	85	78-98	57-126	71-98		71-98	1-126	1-126	
Visit 9 (Week 16)	113	99-126		99-126		99-126			

Visit	Target Day	Time windows for							Hepatitis B viral load	Hepatitis screen, HIV screen, ANA and Anti-ds DNA antibody
		Vital signs	ECG endpoints	Clinical lab testing	Serum Pregnancy test	Urine Pregnancy test	Urinalysis, Serum immunoglobulins			
Visit 10 (Week 20)	141	127-154		127-154		127-154				
Visit 11 (Week 24)	169	155-182	127-210	155-182		155-182	127-210	127-210		
Visit 12 (Week 28)	197	183-210		183-210		183-210				
Visit 13 (Week 32)	225	211-238		211-238		211-238				
Visit 14 (Week 36)	253	239-266	211-308	239-266		239-266	211-308	211-308		
Visit 15 (Week 40)	281	267-294		267-294		267-294				
Visit 16 (Week 44)	309	295-322		295-322		295-322				
Visit 17 (Week 48)	337	323-350		323-350		323-350				1+

Visit	Target Day	Time windows for							
		Vital signs	ECG endpoints	Clinical lab testing	Serum Pregnancy test	Urine Pregnancy test	Urinalysis, Serum immunoglobulins	Hepatitis B viral load	Hepatitis screen, HIV screen, ANA and Anti-ds DNA antibody

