Visit 18 (Week 52)	365	351-378	309-406	351-378		351-406	309-406	>308	
Visit 19 (Week 56)	393	379-406		379-406					
Visit 20 (Week 60)	421	407-434		407-434					
Visit 21 (Week 64)	449	>434	>406	>434		>406	>406		

1-: up to 1st dose date/time; 1+: after 1st dose date/time;

For the efficacy assessment, the reference date for the derivation of relative days of events or findings will be the randomization day. If a patient receives IMP prior to the randomization by mistake, the reference date of efficacy assessment will be the date of the first IMP administration for that patient. For the primary analyses, all available values of scheduled measurements will be assigned to the appropriate visit window according to Table 9. In the event of multiple measurements of the same test in the same window, the one closest to the targeted visit date will be used for the by-visit summary. If they are at the same distance to the target day, the latest one will be used. For the on-treatment sensitivity analyses, only scheduled measurements collected during the treatment epoch will be assigned to a time window.

Table 9 – Time window for efficacy variables

Visit	Target Day	Time windows for		
		Pre-bronchodilator Spirometry, ACQ-5, ACQ-7	Post-bronchodilator spirometry, reversibility	AQLQ(S), EQ-5D-5L, HADS, SNOT-22, RQLQ(S)+12
Visit 1 (Week -4±1)	-28±7	<-14		
Visit 2 (Week 0)	1	-14-1 ¹	1 ¹	1 ¹
Visit 3 (Week 2)	15	1 ⁺ -21	1 ⁺ -21	
Visit 4 (Week 4)	29	22-35	22-42	
Visit 5 (Week 6)	43	36-49		
Visit 6 (Week 8)	57	50-63	43-70	
Visit 7 (Week 10)	71	64-77		
Visit 8 (Week 12)	85	78-98	71-126	1-126
Visit 9 (Week 16)	113	99-126		
Visit 10 (Week 20)	141	127-154		
Visit 11 (Week 24)	169	155-182	127-210	127-210
Visit 12 (Week 28)	197	183-210		
Visit 13 (Week 32)	225	211-238		
Visit 14 (Week 36)	253	239-266	211-308	211-308
Visit 15 (Week 40)	281	267-294		
Visit 16 (Week 44)	309	295-322		
Visit 17 (Week 48)	337	323-350		
Visit 18 (Week 52)	365	351-378	309-406	309-406
Visit 19 (Week 56)	393	379-406		
Visit 20 (Week 60)	421	407-434		
Visit 21 (Week 64)	449	>434	>406	>406

1⁻: up to randomization and before 1st dose date/time; 1⁺: after randomization or 1st dose date/time

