For the pharmacokinetics/pharmacodynamics variables summary, the reference date for the derivation of relative days of measurements will be the date of first IMP administration if the patient is treated with study treatment, or the randomization date if the patient is not treated. Pharmacokinetics /pharmacodynamics variables will be summarized by the analysis window defined in Table 10 for the by visit descriptive analyses. All available values of measurements will be assigned to the appropriate visit window. In the event of multiple measurements of the same test in the same window, the one closest to the targeted visit date will be used for the by-visit summary. If they are at the same distance to the target day, the latest one will be used. For procedures planned on Visit 2, if it is done on the same date as the first IMP injection but the performance time is missing, it will belong to Visit 2 time window.

Table 10 – Time window for pharmacokinetics/pharmacodynamics variables

Visit	Target day	Time windows for					
		Eotaxin-3, ECP, total IgE, TARC	Exhaled NO	Systemic drug concentration	Anti-drug antibodies	Antigen-specific IgE	Periostin
Visit 1 (Week -4±1)	-28±7		<-14				
Visit 2 (Week 0)	1	1-	-14-1-	1-	1-	1-	1-
Visit 3 (Week 2)	15		1+-21	1+-21			
Visit 4 (Week 4)	29		22-56	22-42			1+-56
Visit 5 (Week 6)	43						
Visit 6 (Week 8)	57			43-70			
Visit 7 (Week 10)	71						
Visit 8 (Week 12)	85	1+-126	57-98	71-98	1-126	1-126	57-224
Visit 9 (Week 16)	113		99-126	99-140			
Visit 10 (Week 20)	141		127-154				
Visit 11 (Week 24)	169	127-210	155-210	141-210	127-266	127-266	
Visit 12 (Week 28)	197						
Visit 13 (Week 32)	225						
Visit 14 (Week 36)	253	211-308	211-294	211-308			
Visit 15 (Week 40)	281						
Visit 16 (Week 44)	309						
Visit 17 (Week 48)	337		295-350				
Visit 18 (Week 52)	365	>308	351-378	309-378	267-406	>267	>224
Visit 19 (Week 56)	393		379-406	379-406			
Visit 20 (Week 60)	421		407-434	407-434			
Visit 21 (Week 64)	449		>434	>434	>406		

Visit	Target day	Time windows for					
		Eotaxin-3, ECP, total IgE, TARC	Exhaled NO	Systemic drug concentration	Anti-drug antibodies	Antigen-specific IgE	Periostin
1-: up to 1 st dose date/time or randomization if patient is not treated; 1+: after 1 st dose date/time or randomization date if patient is not treated;							

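### The Week 12 window for PROs, ADA, antigen-specific IgE and HBV load is printed from Day 1, so it overlaps the pre-dose baseline; Day 267 falls in no antigen-specific IgE window (minor)

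*SAP*

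**What the plan says.** SAP section 2.5.4 has three window tables: Table 8 (safety), Table 9 (efficacy) and Table 10 (PK/PD). Each legend gives 1- to values up to first dose (or randomization) and 1+ to values after it. Table 10 words the second as "1+: after 1 st dose date/time or randomization date if patient is not treated".

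The Visit 8 (Week 12) rows read:

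- Table 10: "Visit 8 (Week 12) 85 1+-126 57-98 71-98 1-126 1-126 57-224". After the target day, the columns are the biomarker set (eotaxin-3, ECP, total IgE, TARC), exhaled NO, drug concentration, ADA, antigen-specific IgE and periostin.
- Table 9: "Visit 8 (Week 12) 85 78-98 71-126 1-126". The last column covers AQLQ(S), EQ-5D-5L, HADS, SNOT-22 and RQLQ(S)+12.
- Table 8: "Visit 8 (Week 12) 85 78-98 57-126 71-98 71-98 1-126 1-126". The last two entries are urinalysis with serum immunoglobulins, and hepatitis B viral load.

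The text above Table 10 says "All available values of measurements will be assigned to the appropriate visit window". When several values share a window, the one closest to the target day is used, and the later one if tied. For Table 9, "For the efficacy assessment, the reference date for the derivation of relative days of events or findings will be the randomization day". Section 2.4.4.2.1 adds: "Change from baseline in ACQ-5 and AQLQ at Week 24 will be analyzed using MMRM including change from baseline up to Week 24".

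**The concern.** Visit 2 is Day 1. The PRO questionnaires and the ADA, antigen-specific IgE and (where required) HBV load samples are taken then, before dosing, and each has its own Visit 2 window ending at first dose. A Week 12 window that opens on Day 1 without the plus sign overlaps that baseline window.

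If the tables are programmed as printed, one value can serve as both baseline and Week 12 result. That is baseline carried forward, which the SAP does not plan anywhere. What is at stake is the Week 12 change in the PROs, who is counted at Week 12 in the by-visit ADA table and plot, and the Week 12 descriptive summaries of antigen-specific IgE and HBV load.

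**Working it through.** The plan states no figure to reproduce. The check applies its window rule to the printed bounds.

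**1. Is 1-126 out of line with the other columns?** These are the first post-baseline windows in each table:

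| Table | Starts at 1+ | Printed 1-126 |
|---|---|---|
| 8 | vital signs, ECG, clinical labs, urine pregnancy test, hepatitis/HIV/ANA screen | urinalysis/immunoglobulins; HBV load |
| 9 | pre-bronchodilator spirometry with ACQ; post-bronchodilator spirometry | AQLQ, EQ-5D-5L, HADS, SNOT-22, RQLQ |
| 10 | biomarker set, exhaled NO, drug concentration, periostin | ADA; antigen-specific IgE |

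The five columns in the right-hand list are the only exceptions. Urinalysis and immunoglobulins are sampled at Visit 1 and not at Visit 2, so no scheduled Day 1 value is at risk there.

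**2. When does the Day 1 value win?** The target is Day 12 × 7 + 1 = 85.

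- Distance of Day 1 from target: |1 − 85| = 84.
- Largest distance among Days 2 to 126: |2 − 85| = 83 (Day 126 is at 41).

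Since 83 < 84, any value on Days 2 to 126 displaces the Day 1 value.

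| Values available | Week 12 value with 1-126 | Week 12 value with 1+-126 |
|---|---|---|
| Day 1 and Day 85 | Day 85 | Day 85 |
| Day 1 and Day 2 | Day 2 | Day 2 |
| Day 1 only | Day 1, change 0 | missing |
| Day 1 and Day 130 | Day 1, change 0 | missing |

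The two versions differ only for a patient with a Day 1 value and nothing on Days 2 to 126.

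**3. Do other rules close the gap?** The closest-to-target rule does not help when Day 1 is the only candidate. Tables 8 and 10 send a same-day sample with no recorded time to Visit 2, but that covers only untimed samples and is absent from the text for Table 9. No sentence says that a value placed at Visit 2 cannot also fill Visit 8.

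**4. Size.** If a fraction q of an arm has only the Day 1 value and the others have mean change d, the simple Week 12 mean becomes (1 − q) × d + q × 0 = (1 − q)d. The documents give no q.

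**5. Where it lands.**

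- PROs: the Week 12 change is a listed secondary endpoint, estimated by MMRM, so inserted zeros enter directly. The AQLQ responder analysis at Week 12 is unaffected, because zero change and missing both count as non-response.
- ADA: treatment-emergent status requires a positive result after first dose (SAP 2.1.6), and the ADA population requires a result after first dose (SAP 2.3.3). Only a Week 12 denominator is open to the error, for a patient first sampled after Day 126.
- Tested AQLQ: Table 6 tests it at Week 24, whose window is 127-210. A spurious Week 12 zero can reach it only as an extra response in the model.

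**6. Day 267.** Antigen-specific IgE runs 127-266 at Visit 11, then >267 at Visit 18, so Day 267 is unassigned. Neighbouring columns adjoin correctly: ADA resumes at 267, the biomarker set goes 211-308 then >308, and periostin 57-224 then >224.

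**The case against.** The strongest objection is that the plus sign may simply have been lost when the SAP was read from PDF. Superscripts are damaged elsewhere: the Visit 2 cells of Table 9 show a raised 1 where the legend defines a raised minus. This cannot be excluded, so the printed cells must be checked. It is unlikely, because 1+ survives in all three tables, including the same Table 10 row. The Day 267 gap does not depend on a superscript at all.

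A second objection is that the SAP already gives the pre-dose value to Visit 2, speaks of one appropriate window, and defines baseline separately as the last value before first dose. That shows the intent, and a careful programmer would probably follow it. It does not remove the overlap from an operative table.

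Third, few patients can be affected. Patients who stop treatment have an early-discontinuation visit that includes the PROs, ADA and antigen-specific IgE (protocol section 1.3), and AQLQ and ADA remain scheduled at Week 12 afterwards. This stands, and it is why the point is minor.

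A reader might infer that confirmatory steps 19, 20, 24 and 25 of Table 6, all on AQLQ, are directly biased. The documents do not support that, since the Week 24 window does not include Day 1. Nor do they support an inference that treatment-emergent ADA is miscounted, since a pre-dose sample cannot qualify.

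**Conclusion.** As printed, the Week 12 window overlaps the pre-dose baseline on Day 1 for AQLQ, EQ-5D-5L, HADS, SNOT-22, RQLQ, ADA, antigen-specific IgE and HBV load. A patient with no value on Days 2 to 126 would then have the baseline repeated as Week 12. The effect is small, and its size cannot be derived from the documents. It touches the Week 12 PRO estimates, possibly the by-visit ADA denominator (SAP 2.4.6.1.2 does not define it), and descriptive IgE and HBV summaries. It reaches the tested Week 24 AQLQ only indirectly. Day 267 is a separate one-day gap in a descriptive summary.

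This rests on three assumptions: the PDF cells match the text, the tables are programmed literally, and Table 6 is the operative testing list. The protocol synopsis still names AQLQ at Week 12 among its first secondary tests, while SAP Table 6, described as the complete list, tests it at Week 24. The severity is minor.

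**What to change.** First confirm the cells in the SAP PDF. If they read as above, change the Visit 8 window from 1-126 to 1+-126 for:

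- ADA and antigen-specific IgE in Table 10;
- AQLQ, EQ-5D-5L, HADS, SNOT-22 and RQLQ in Table 9;
- HBV load in Table 8, with the urinalysis/immunoglobulin column changed for consistency only.

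In Table 10, change the Visit 18 window for antigen-specific IgE from >267 to >266.

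The cost is an edit to three SAP tables and the matching window code before database lock. No data collection or model changes, and there is no analytical downside.

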2.5.5 Unscheduled visits

Unscheduled visit measurements of laboratory data, vital signs, and ECG will be included in the by-visit summaries, computation of baseline, worst values, and PCSAs.

2.5.6 Pooling of centers for statistical analyses

Due to the large number of centers, the randomization is stratified by country. Due to small sample size in some countries, the countries will be pooled into regions as defined below for the analyses:

- East Europe: Hungary, Poland, Russia, Turkey and Ukraine
- Western Countries: Australia, Canada, France, Germany, Italy, South Africa, Spain, United Kingdom and USA
- Asia: Japan, South Korea and Taiwan;
- Latin America: Argentina, Brazil, Colombia, Chile and Mexico

2.5.7 Statistical technical issues

None.

3 INTERIM ANALYSIS

No interim analysis is planned.

4 DATABASE LOCK

The database lock is planned based on the time when approximately 1638 patients (originally planned sample size) complete Week 52 visit or discontinue from the study before Week 52. Analyses will be based on all data collected up to this database lock and will be considered as the final analyses in the CSR. Additional data between database lock and last patient completing last visit will be summarized in CSR addendum.

5 SOFTWARE DOCUMENTATION

All summaries and statistical analyses will be generated using SAS version 9.4 or higher.

